#### 6.4. STUDY DESIGN

This single-subject case series will utilize an ABA design, where the intervention phase (b) is sandwiched between an initial baseline period (a) and post-intervention/return-to-baseline period (a). Each baseline period will last for one-week and involve unrestricted standard care. The intervention period will last for three-weeks, allowing a one-week acclimatization period before a two-week full-scale wearing protocol (if tolerable to the child). The full-scale wearing protocol was defined – through analysis of existing testimonial data, and consultation with JettProof and prescribing clinicians – as a minimum 6 hours/day of continuous wear. The participants will comprise children aged 4 years 0 months to 11 years 11 months with an existing community diagnosis of autism spectrum disorder (see Section 6.8. for a full description of trial inclusion/exclusion criteria). Child participants will attend six face-to-face assessment sessions with their caregiver(s): upon study entry (week 0), during pre-intervention/baseline phase A (week 1), pre-intervention/acclimatization phase B (week 2), intervention phase A (weeks 3 and 4), and post-intervention/return to baseline phase A (week 5).

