## 6.7. OUTCOMES

### 6.7.A. PRIMARY OUTCOMES

The primary outcomes for this trial are:

- Child sympathetic nervous system activity (i.e., heart rate, heart rate variability, electrodermal activity, and motion-based activity) acquired from an Empatica E4 wristband, worn in the context of Laboratory Temperament Assessment Battery (Lab-TAB; H. Goldsmith et al., 2010) episodes conducted in weeks 1 through 5. Empatica E4 recordings have been shown to accurately predict affective behaviour in autistic children (Goodwin, Mazefsky, Ioannidis, Erdogmus, & Siegel, 2019) and has been validated against other stationary and wearable biosensors (Schuurmans et al., 2020; van Lier et al., 2020).
- Child motor coordination as measured by the standardized Movement Assessment Battery for Children-2nd Edition (M-ABC-2; Henderson, Sugden, & Barnett, 2007) and Clinical Observations of Motor and Postural Skills (COMPS-2; B Wilson, Kaplan, Pollock, & Law, 2000) in weeks 1 and 5. The M-ABC-2 is one of the most widely used motor assessments in research and clinical practice (Barnett, 2008) with evidence of inter-rater reliability, test-retest reliability, content- and concurrent validity (Henderson et al., 2007). The COMPS-2 was designed to supplement standardized measures of motor performance and has demonstrated good inter-rater reliability, test-retest reliability, and construct validity (Brenda Wilson, Pollock, Kaplan, Law, & Faris, 1992).
- Child attainment of individualized and meaningful intervention goals as measured by Goal Attainment Scaling (GAS; Kiresuk & Lund, 1994). Upon study entry, the caregiver of each child will be supported by investigators to formulate two GAS goals centred around self-regulation difficulties for their child and develop a five-point descriptive rating scale for completion in weeks 1 and 5. Use of GAS is common in research and clinical practice and is especially sensitive to capturing change in intervention studies (McLaren & Rodger, 2003).

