#### *6.8.C. ASSESSMENT SCHEDULE*

Child participants will attend six face-to-face assessment visits (See Figure 1 & Table 1) with their caregiver(s) during each of the trial weeks. Assessment visits at weeks 1 through 5 will each involve a researcher fitting the child with an Empatica E4 wristband on the wrist or calf. Empatica E4 recordings will be taken while children watch a low-demand movie (Inscapes) to ascertain their physiological baseline, and while completing Lab-TAB (H. Goldsmith et al., 2010) episodes interspersed with a period

of free-play with their caregiver. Additional assessments conducted at weeks 1 and 5 include the M-ABC-2 and COMPS-2, and at week 5 an examiner-led interview to explore child and caregiver perceptions and experiences of the singlet. All assessment sessions will be video-recorded with consent from caregivers for later scoring.

The caregiver will be given a laptop during each of their child's assessment visits and navigated to a REDCap survey to complete: GAS (Kiresuk & Lund, 1994) in weeks 1 through 5, in addition to the SCAS-P (Nauta et al., 2004), PES (Pfeiffer et al., 2017). Additionally, the PSI-4-SF (Abiden, 2012) will be completed via hardcopy in weeks 1 and 5. Caregivers who do not manage to complete all survey measures during their child's assessment visit will be provided a survey return code, enabling them to return to the survey for later completion (within 24 hours). The PSI-4-SF may be taken home for completion and return at the child's next assessment visit. Assessment visits in Weeks 2, 3 and 4 will require a time commitment of around one hour for children and their caregiver(s). A longer time commitment of two hours will be required for visits in Weeks 1 and 5.

During the trial period, the caregiver will receive a push notification on their smartphone from their installed MyCap application three times per day (morning, afternoon, evening) to report their child's previous night's sleep (morning, only), current activity, affect, use of non-routine medications (evening, only), and singlet wearing (intervention phases, only). The resulting daily time commitment for caregivers will be approximately 6 minutes (2 minutes per day).

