## 7.3. STATISTICAL METHODS

### 7.3.A. OUTCOME ANALYSES

This single-case feasibility study will combine visual and quantitative analyses of the data. For each participant, scores for each repeated outcome measure (i.e., Empatica E4 recordings, Lab-Tab, GAS, PES-H, PES-C, PSI-4-SF) will be graphically depicted as a time-series with standard deviation bands around each series and the global average for each outcome measure plotted as a reference line. Visual analysis will be employed for an initial examination of within-subject slope and level change across trial phases. Effect sizes will be computed through parametric methods (i.e., standard mean difference [Hedges *g*]) and non-overlap indices (e.g., Tau-U), with a *p*-value of < .05 indicative of statistical significance.

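### With 1, 3 and 1 weekly scores per child, the p < .05 rule in Section 7.3.A does not fit the schedule: a two-sided A-versus-B Tau cannot go below .083, and Hedges g is zero or undefined for two key contrasts

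*Protocol*

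**What the plan says.** Section 6.4 fixes the phases. For phase A, "Each baseline period will last for one-week and involve unrestricted standard care". For phase B, "The intervention period will last for three-weeks, allowing a one-week acclimatization period before a two-week full-scale wearing protocol". Section 6.8.C sets one visit per trial week: "Assessment visits at weeks 1 through 5 will each involve a researcher fitting the child with an Empatica E4 wristband". Section 6.7.A ties the E4, a primary outcome, to Lab-TAB "episodes conducted in weeks 1 through 5".

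GAS, also primary, is rated weekly in Section 6.8.C and Table 1, but only in weeks 1 and 5 in Section 6.7.A. PES and PSI-4-SF are taken in weeks 1 and 5 only (Section 6.7.C, Table 1).

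Section 7.3.A names E4, Lab-TAB, GAS, both PES versions and PSI-4-SF as repeated measures. The plots are made per child ("For each participant, scores for each repeated outcome measure"), and changes of slope and level are judged within the child. Hedges g and "non-overlap indices (e.g., Tau-U), with a *p*-value of < .05 indicative of statistical significance" follow. The section does not state the contrast, sidedness, Tau-U variant, exact or asymptotic p, the test behind g, or whether effect sizes are per child or pooled.

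**The concern.** A significance rule is useful only if the data can meet it when the effect is real and fail it when it is not. Here each A phase holds a single weekly score. One point has no slope and no SD, so baseline slope, baseline variability and any baseline-trend correction are out of reach, whatever a later analysis plan says. PES and PSI-4-SF have no phase B score at all, so no A-versus-B index exists for them.

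Two primary outcomes (E4 and GAS) are affected, and this is the protocol's only inferential rule. Section 6.9 gives preliminary effect sizes as a purpose of the trial, yet g is unusable for baseline against full-scale wear and for pre against post. Non-significance forced by the schedule could be read as no effect, and significance could come from the choice of index.

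**Working it through.** **Inputs.** Phases of 1, 3 and 1 weeks (Section 6.4), one visit per week (Section 6.8.C, Table 1), and threshold .05 (Section 7.3.A). One score per visit per variable is an assumption. The protocol has no power calculation to reproduce, but its visit count checks out: 2+2+1+1+1+2 = 9 hours for six visits, and 3 × 2 min × 35 days = 3.5 hours of experience sampling, both as in the Synopsis.

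**Tau, complete separation.** S = nA·nB; SD = √[nA·nB(nA+nB+1)/3]; z = S/SD. Exact two-sided p = 2/C(nA+nB, nA), capped at 1.

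| Contrast | nA v nB | z | p, normal | p, exact |
|---|---|---|---|---|
| Weeks 1+5 v 2-4 | 2 v 3 | 6/3.464 = 1.73 | .083 | 2/10 = .20 |
| Week 1 v 2-4 | 1 v 3 | 3/2.236 = 1.34 | .18 | 2/4 = .50 |
| Week 1 v 3-4 | 1 v 2 | 2/1.633 = 1.22 | .22 | 2/3 = .67 |
| Week 1 v week 5 | 1 v 1 | 1/1 = 1.00 | .32 | 1.0 |

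Combining week 1 v B with B v week 5 as if independent gives z = 1.90, p = .058, still above .05.

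**Hedges correction.** J = 1 − 3/(4·df − 1), df = nA + nB − 2.
- 1 v 2: df = 1, J = 1 − 3/3 = 0, so g = 0 whatever the data.
- 1 v 1: df = 0, no within-phase SD, g undefined.
- 1 v 3: df = 2, J = 1 − 3/7 = .571.
- 2 v 3: df = 3, J = 1 − 3/11 = .727.

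**Routes below .05.**
- Tau-U with phase B trend, 1 v 3, fully monotone: S = 6, SD = √(4·3·13/18) = 2.944, z = 2.04, p = .0415; exact 2/24 = .083.
- The same index on pooled A phases with the A trend subtracted and all ten pairs aligned: z = 2.45, p = .014; exact 2/120 = .017. It treats weeks 1 and 5 as adjacent and needs week 5 to lie further from phase B than week 1.
- One-sided pooled A v B: normal .042, exact .10.
- t-test: |d| must exceed t(.975, df)·√(1/nA + 1/nB), which is 4.97 for 1 v 3 and 2.91 for 2 v 3.
- Task-level scores treated as independent (number per visit assumed): 2 per visit, 2 v 6, p = .046; 3 per visit, 3 v 9, p = .013.

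**Across children.** One contrast per child and an exact sign-flip test have a smallest two-sided p of 2/2^10 = .002 with all ten children. Six children still allow 2/64 = .031; five do not (2/32 = .0625).

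**Drift.** Mean(2,3,4) = 3 = mean(1,5), and 0.375×1 + 0.625×5 = 3.5 = mean(3,4), so both contrasts in the fix cancel linear drift. Week 1 against weeks 2-4 does not: 0.1 SD per week biases it by 0.1 × (3 − 1) = 0.2 SD. A one-off drop h after week 1, then flat, leaves a bias of size h − h/2 = h/2 in the first contrast and h − 0.625h = 0.375h in the second.

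**The case against.** A reader might infer that no child can ever reach significance on a weekly outcome, however large the effect. The documents do not support that. Section 7.3.A leaves sidedness, index and contrast open and names Tau-U only as an example; the routes listed above do go below .05, and the t-test responds to effect size. Hedges g is also defined for 1 v 3 and 2 v 3, though heavily shrunk. What stands is that these routes are fragile: they use 2 or 3 degrees of freedom, lean on a normal approximation at four or five points, mix trend within phase B into the phase contrast, or ignore dependence within a visit.

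The per-child unit is inferred, since the effect-size sentence does not name one. Pooling ten children at 1 v 3 gives z = 4.24. Per child remains the natural reading, because Section 6.2 compares each participant with their own baseline. One score per visit is likewise an assumption: Table 2 lists Lab-TAB task scores beside a composite.

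It is also tempting to call the plotted bands, "with standard deviation bands around each series and the global average for each outcome measure plotted as a reference line", worthless. In five points none can lie more than 4/√5 = 1.79 SD from the mean, but no band width is given and a 1 SD band can be crossed.

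Finally, this is a feasibility study that begins with visual analysis, and many of these details may properly sit in a statistical analysis plan. That lowers the severity. It does not remove the point, because no analysis plan can add baseline visits.

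**Conclusion.** The point holds in limited form and should be fixed; it is not fatal to the trial. With one score per visit and a per-child, two-sided, plain A-versus-B comparison, p < .05 is out of reach: the floor is .083 (exact .20) for the most favourable single contrast and .18 (exact .50) for week 1 against weeks 2-4. Hedges g is identically 0 for baseline against full-scale wear and undefined for pre against post. PES and PSI-4-SF have no phase B value. GAS has 1, 3 and 1 scores only on the Section 6.8.C and Table 1 schedule; on the Section 6.7.A schedule it too has none in phase B. That null results are certain, or would be reported as evidence of no effect, goes beyond the text. The thrice-daily experience sampling, about 21, 63 and 21 ratings by phase, is not affected, but Section 7.3.A does not list it among the repeated measures.

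**What to change.** In Section 7.3.A:
- Drop p < .05 for within-child weekly and pre-post series; report raw values and raw phase differences descriptively.
- For E4, Lab-TAB and GAS, pre-specify one contrast per child that uses both A phases: either mean(weeks 2-4) − mean(weeks 1, 5), or, leaving out acclimatization, mean(weeks 3-4) − (0.375 × week 1 + 0.625 × week 5). Define the one score per visit that enters it.
- Estimate the contrast across the 10 children with a 95% CI and an exact sign-flip test. State that it removes linear drift only and not a one-off habituation drop after week 1.
- Analyse PES and PSI-4-SF as week 5 minus week 1 change across children, noting that both are standard-care weeks.
- Reserve within-child Tau-U for the daily experience-sampling series, and add that series to the list.
- Reconcile the GAS schedule between Section 6.7.A and Section 6.8.C with Table 1.

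The cost is wording only, with no new visits or measures. Within-child significance claims on weekly outcomes are given up, and the test then speaks to the average over children; individual response rests on the plots and raw differences.

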## 6.2. CHOICE OF COMPARATORS

This single-subject case series will compare each participant's response to the intervention against their own baseline. No concomitant care or intervention is prohibited during the trial; rather, participants will continue their standard care with the addition of the intervention during the second, third and fourth trial weeks. The single-subject design is advantageous for intervention research with the autistic population in accounting for heterogeneity of clinical/phenotypic presentation and responsiveness to intervention –which otherwise impede firm conclusions in large-scale controlled trials that appraise intervention effectiveness at the group level. Moreover, by utilizing a single-subject design and the comparator of standard care, this research project will have ecological validity – i.e., mirroring 'real world' implementation by clinicians alongside other eclectic interventions – and generate findings that are relevant to clinical practice and policy. Other branded sensory garments or alternative sensory-based therapies were not included as comparators at this preliminary stage of evaluation and hypothesis generation.

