## 6.3. OBJECTIVES

This study will test the use of JettProof sensory singlets among children with a diagnosis of Autism Spectrum Disorder. The primary objective of this trial is to evaluate the effects of JettProof sensory singlets – applied for at least 6 hours/day for a three-week period – on the self-regulatory and motor functioning of autistic children. We hypothesise that application of the JettProof sensory singlet will lead to a reduction in autonomic and behavioural markers of affective and motor dysregulation and the subsequent attainment of individualized goals, relative to standard care.

A second objective is to evaluate the effects of JettProof sensory singlets on additional outcomes related to sensory and motor functioning difficulties for autistic children and their caregivers. We hypothesize that, for children, the application of the JettProof sensory singlet will lead to a reduction in anxiety, less negative and more positive daily affect, and improvements in sleep quality for children and, for caregivers, a reduction in the levels of stress and perceived effort required to assist their children.

A third objective is to assess the feasibility and acceptability of implementing JettProof sensory singlets with autistic children. We anticipate that most children will wear the singlet for 6 hours/day or more during the full-scale intervention phase, and report that it is at least tolerable.

A fourth, exploratory objective is to determine whether there may be sensory characteristics of autistic children that predict differential response to JettProof sensory garments. We hypothesize that JettProof sensory singlets will evidence greater efficacy among children with a dysfunction in proprioceptive and/or vestibular sensory systems.

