## 8.8. DISSEMINATION POLICY

### 8.8.A. TRIAL RESULTS

Findings from this trial will be disseminated via a manuscript submission to a peer-reviewed journal, traditional and social media outlets, and at academic and professional conferences. JettProof may communicate trial results to the public provided that this is not misleading and there is no disclosure of confidential information. There are no publication restrictions.

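### Section 7.3.A calls any p < .05 significant across at least seven unranked primary variables, so the stated threshold does not carry a 5% error rate

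*Protocol*

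**What the plan says.** Section 6.7.A opens with "The primary outcomes for this trial are" and gives three bullets without ranking them. The first bullet alone holds four variables: "Child sympathetic nervous system activity (i.e., heart rate, heart rate variability, electrodermal activity, and motion-based activity) acquired from an Empatica E4 wristband". The second names two motor instruments, M-ABC-2 and COMPS-2. The third is Goal Attainment Scaling (GAS). The registry data set in Section 2.2.B repeats the three outcomes, also unranked.

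Section 7.3.A begins with plots for each participant and visual analysis. It then computes effect sizes by a parametric method (Hedges g) "and non-overlap indices (e.g., Tau-U"), "with a *p*-value of < .05 indicative of statistical significance". The sentence does not say whether the p-value is computed within each child or across the ten. It names no lead variable or lead index.

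On purpose, the protocol speaks in two voices. Section 6.2 places the trial "at this preliminary stage of evaluation and hypothesis generation", and Section 6.9 justifies ten participants by feasibility, preliminary effect sizes and practical limits. Yet the title refers to effectiveness, and Section 6.3 states a directional primary hypothesis of "a reduction in autonomic and behavioural markers of affective and motor dysregulation and the subsequent attainment of individualized goals, relative to standard care".

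**The concern.** A fixed .05 threshold means what it says for one pre-named test. Here it is attached to every primary variable and to more than one method, with nothing to show which result decides the primary hypothesis. A reader of the results would take a significant primary finding to have a 1 in 20 chance of arising with no effect. That would not be true.

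This matters outside the research team. Section 8.8.A plans publication and states that "JettProof may communicate trial results to the public provided that this is not misleading and there is no disclosure of confidential information". The proviso about misleading statements is a real safeguard, but it is hard to apply when the protocol itself calls each such result statistically significant. Section 8.8.C plans no public access to the full protocol or the code, so an outside reader could not count the tests behind a reported signal.

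**Working it through.** **Inputs from the protocol.** Threshold .05 per test, no adjustment stated (7.3.A). Primary variables: 4 wristband + 2 motor + 1 GAS = 7 (6.7.A); Table 2 adds component or domain scores for the motor tests, so seven is a minimum. Ten children (6.9). Wristband recordings at weeks 1 to 5; motor tests at weeks 1 and 5 only (6.8.C, Table 1). GAS at weeks 1 and 5 in 6.7.A, but weeks 1 through 5 in 6.8.C and Table 1. Weeks 1 and 5 are A phases; weeks 2 to 4 are the B phase, including acclimatization.

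**Assumptions.** Two-sided tests, because sidedness is not stated. Correlation between variables is not given, so a range is shown. One summary score per visit. No true effect on any variable. The protocol states no familywise error rate, so there is no figure of its own to reproduce.

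**Group level, one test per variable.** With independent tests, the chance of at least one false positive is 1 − 0.95^7 = 1 − 0.698 = 30.2%. For correlated variables, paired t tests were simulated with n = 10 and 20,000 replicates. A signed-rank test on the same data stood in for a second method.

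| Correlation | One method | Either of two methods |
|---|---|---|
| 0 | 30.2% | 33.6% |
| 0.3 | 27.9% | 30.8% |
| 0.5 | 23.8% | 26.3% |
| 0.8 | 16.1% | 17.9% |
| 0.95 | 9.9% | 11.4% |

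Over correlations 0 to 0.8, one method gives 16.1/5 = 3.2 to 30.2/5 = 6.0 times the stated rate. Even at 0.95 the rate is about twice 5%. Counting two methods as 14 independent tests would give 1 − 0.95^14 = 51.2%, which overstates the problem because both use the same scores.

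**Child level, if that is the unit.** M-ABC-2 and COMPS-2 have no B-phase score, so neither gives a within-child A-versus-B test. That leaves four wristband signals and, if rated weekly, GAS: at most five variables. A t test of 2 A against 3 B points on five variables in ten children was simulated with 10,000 replicates. The chance of at least one false positive somewhere is:

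- correlation 0: 92%
- correlation 0.5: 90%
- correlation 0.8: 82%
- correlation 0.95: 66%

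The independent-test formula agrees: 1 − 0.95^50 = 92.3%. If GAS is rated only at weeks 1 and 5, four variables remain: 1 − 0.95^40 = 87.1%. Serial correlation of 0.3 between weeks raises the simulated figures by about one percentage point.

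**Tau-U within one child.** Take the simple A-versus-B non-overlap comparison, without trend correction, with 2 A and 3 B weekly scores. The smallest exact two-sided p is 2/C(5,2) = 2/10 = .20. By normal approximation, the largest S is 2 × 3 = 6 and Var(S) = 2 × 3 × 6/3 = 12, so z = 6/√12 = 1.73 and p = .083. With 1 A against 3 B the minima are .50 exact and .18 normal. None reaches two-sided .05. A one-sided normal approximation for 2 against 3 could just reach .042.

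**The case against.** The strongest reply is that this is a feasibility study. Section 7.3.A says so in its first sentence, puts visual analysis first, and Section 6.9 asks only for preliminary effect sizes. Nowhere does the protocol say that one significant signal, index or child would establish the hypothesis. Multiplicity detail may also sit in a statistical analysis plan that is not shown. Much of this stands, and the missing adjustment method is not held against the protocol here. What remains is what the protocol itself fixes: unranked primaries and a bare significance rule. An analysis plan would have to override that text, and the feasibility aim is a reason to drop the threshold.

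A reader might go further and infer that a chance significant primary result is close to certain. Seventy independent tests (seven variables in ten children) would give 1 − 0.95^70 = 97.2%, and two independent methods (140 tests) 99.9%. The protocol does not support this:

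- In Section 7.3.A the reference to each participant governs the plots; the effect-size sentence names no unit.
- The motor tests cannot be compared between A and B within a child.
- Two-sided Tau-U on weekly scores cannot add false positives within a child.
- Daily ratings are secondary outcomes (6.7.B), so they cannot produce a false primary result.
- Splitting wristband recordings into epochs would make more per-child tests possible, but no section states that analysis.

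**Conclusion.** Wrong as written. The p < .05 rule in Section 7.3.A does not give a 5% chance of a false significant primary result. The supported size is about 16% to 30% for one group-level test per variable (correlation 0.8 to 0), and up to about 34% with a second method on the same data. The 66% to 92% range is conditional on parametric testing within each child on weekly scores with five testable primaries; its lower end uses a correlation of 0.95. The unit of testing, its sidedness and the correlations are assumptions, since the protocol states none of them. The direction of the conclusion does not depend on them: every scenario computed for the full set of primaries exceeds 5%. The feasibility aim limits the consequence. The data remain usable as preliminary estimates, and the fault lies in the label attached to them.

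**What to change.** In Section 7.3.A, replace "with a *p*-value of < .05 indicative of statistical significance" with a statement such as: effect sizes, with confidence intervals where the number of observations allows, are descriptive; p-values are exploratory, are not adjusted for multiplicity, and will not be used to claim effectiveness. The condition on intervals is needed because a single child contributes only one to three weekly scores per phase.

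If one inferential claim is wanted, name in Sections 6.7.A and 7.3.A one lead primary variable measured in both A and B phases and one index in place of the open list. Summarise that index over the ten children, test only that at two-sided .05, and list the other primaries as supportive. The motor tests do not qualify as lead on the present schedule. GAS qualifies only once its timing is reconciled between Section 6.7.A and Section 6.8.C with Table 1. Bonferroni over seven variables (.05/7 = .0071 per group-level test) would also hold the familywise rate, but suits ten children poorly.

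The cost is wording, with no new data or visits. The downside is that results on a single signal or a single child can no longer be called statistically significant.
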